3.6 SARI patient identification – algorithm for patient inclusion

SARI patients are identified from among patients hospitalised for at least 24 hours in one of the participating hospitals. SARI patients should be enrolled and swabbed within 48 hours of hospital admission.

3.6.1 Recruitment strategies

[figure not shown]
For hospitals with electronic patient records and/or diagnosis codes commonly displayed, SARI-related ICD codes (or other codes used for SARI surveillance) may be used. Patients admitted with any of the ICD codes listed in Table 3 will be approached; those meeting the SARI case definition and the inclusion criteria will be invited to be part of the study and give consent, if required by the country's legislation (Figure 1).

Figure 1. Proposed inclusion algorithm for hospitals/services relying on common use of ICD codes, hospital-based COVID-19/influenza vaccine effectiveness study

For hospitals where ICD codes on admission are not systematically collected or accessible, all patients will be systematically screened. This should be done by sensitising the medical staff at the beginning of the study (Figure 2) and following up with regular study coordinator reviews.

Figure 2. Proposed inclusion algorithm for hospitals/services systematic screening of all admitted patients, hospital-based COVID-19/influenza vaccine effectiveness study

Retrospective recruitment (or 'catching-up' on already diagnosed patients) is not recommended for the CVE study, as not all COVID-19 patients exhibit SARI symptoms and it will be difficult to determine the reasons for testing retrospectively.

Each study site/country to describe procedures used to identify study participants.

In the event of test scarcity, extreme workload, or budget limiting inclusion to a threshold of patients, the study sites/countries may need to switch from exhaustive to systematic sampling (e.g. inclusion of patients every second day, or only on certain days in the week). Forward planning should be undertaken by the study sites for systematic sampling procedures. During the period of systematic selection, the study sites should make sure that they document the sampling fraction.

- Where a study site/country is not testing all SARI cases to describe the systematic sampling procedure, if systematic sampling is not being carried out, the criteria for testing should be explained.
- > Each study site/country using ICD-10 codes for case identification should list the codes used.

Table 2. Diagnosis codes for which patients could be screened for onset of SARI symptoms, COVID-19/influenza in hospital-based VE studies

Category	Morbidity	ICD-9	ICD-10
Influenza-like illness	Cough	786.2	R05
	Difficulty breathing	786.05	R06
	Sore throat	784.1	R07.0
	Dysphagia	787.20	R13
	Fever	780.6	R50.9
	Headache	784.0	R51
	Myalgia	729.1	M79.1
	Fatigue/malaise	780.79	R53.1, R53.81, R53.83
Cardiovascular	Acute myocardial infarction/acute coronary syndrome	410-411, 413-414	120-23, 124-25
diagnosis	Heart failure	428 to 429.0	I50, I51
Respiratory diagnosis	Emphysema	492	J43.9
	Chronic obstructive pulmonary disease	496	J44.9
	Asthma	493	J45
	Myalgia	729.1	M79.1
	Dyspnoea/respiratory abnormality	786.0	R06.0
	Respiratory abnormality	786.00	R06.9
	Shortness of breath	786.05	R06.02
	Tachypnoea	786.06	R06.82
	Other respiratory abnormalities	786.09	R06.00, R06.09, R06.3, R06.89
Infections	Pneumonia and influenza	480-488.1	J09-J18
	Other acute lower respiratory infections	466, 519.8	J20-J22
	Viral infection, unspecified	790.8	B34.9
	Bacterial infection, unspecified	041.9	A49.9
	Myocarditis	429.0	140.9
	Bronchitis	490, 491	J40, 41
Inflammation	SIRS* non-infectious without acute organ dysfunction	995.93	R65.10
	SIRS* non-infectious with acute organ dysfunction	995.94	R65.11
	Vomiting	787.0	R11
Abdominal symptoms	Diarrhoea	009.3, 787.91	A07.9, K52.9
• •	Abdominal pain	789.0	R10
	General physical deterioration, lethargy, tiredness	780.79	R53.1, R53.81, R53.83
	Anorexia	783.0	R63.0
	Feeding difficulties	783.3	R63.3
	Abnormal weight loss	783.21	R63.4
Diamana malata dita	Other symptoms/signs concerning food and fluid intake	783.9	R63.8
Diagnoses related to deterioration of	Disorientation/altered mental status	780.97	R41.0
general condition or	Dizziness and giddiness	780.4	R42
functional status	Infective delirium	293.0, 293.1	F05
יעויטווטוימו אמנעא	Coma	780.01	R40.2
	Transient alteration of awareness	780.02	R40.4
	Other alteration of consciousness (somnolence, stupor)	780.09	R40.0, R40.1
	Febrile convulsions (simple), unspecified	780.31	R56.00
	Complex febrile convulsions	780.32	R56.01
Other	Anosmia, ageusia, myalgia	781.1, 729.1	R43.0, R43.2, M79.1

^{*} SIRS: Systemic inflammatory response syndrome

3.7 Laboratory methods

Study nurses or physicians will collect respiratory specimens (see Section 4.4) from all eligible patients, respecting safety standards for COVID-19 and influenza, and following WHO biosafety guidelines.⁷

> Each study site/country to describe the type (nasopharyngeal/oropharyngeal or both) and number of swabs taken for each patient.

Influenza laboratory confirmation will be done using RT-PCR or multiplex RT-PCR. Specimens will undergo molecular analysis for currently circulating influenza viruses.

PCR should be run with the inclusion of an internal/external quality control. It is recommended that the quality of the samples be monitored using an internal control to check for the presence of human cells in respiratory specimens.

⁷ Any non-propagative diagnostics (e.g. sequencing, RT-PCR) should be conducted at a facility using procedures equivalent to biosafety level 2 (BSL-2), while propagative work (e.g. virus culture, isolation or neutralisation assays) should be conducted at a containment laboratory with inward directional airflow (BSL-3). Patient specimens from suspected or confirmed cases should be transported as UN3373, 'biological substance category B'. Viral cultures or isolates should be transported as category A, UN2814, 'infectious substance, affecting humans'[32].

ECDC's recommendation for SARS-CoV-2 laboratory confirmation is by viral RNA detection with nucleic acid amplification tests, such as RT-PCR. Specimens will undergo molecular analysis for currently circulating SARS-CoV-2 virus. During the influenza season, influenza virus tests will also be performed (and this is also recommended for countries not performing IVE), provided that there is circulation of influenza viruses in the community [30,31]. This is especially important to identify any potential association between influenza and SARS-CoV-2.

Following the procedures outlined by each study, all or a systematic sample of the detected viruses will undergo gene sequencing. The sampling procedure can include sequencing all viruses, or a systematic sample. The systematic sample should be representative of cases and be large enough to provide reasonable precision when calculating proportions of virus change over time. Guidance on random sampling for selection of samples for sequencing is provided in Annex 3.

If sequencing is performed, gene sequences should also be uploaded to GISAID's open access EpiCoV or EpiFlu platform (https://gisaid.org/ and raw WGS data should be uploaded to the EU portal (ENA) database). Gene sequence information can be provided directly to the coordinating central hub for the study, or the GISAID EpiCoV/EpiFlu accession number can be provided alongside the study's unique identifier to link these data (see Annex 3, after the section on random sampling). Processed genetic information (e.g. name of genetic clade) can also be included within the epidemiological database. The proportion of specific COVID-19 subvariants may be used to define a subvariant dominating period (e.g. >= 90% of isolates of a specific subtype during a defined period) [21-24].

- > Each study site/country to describe the laboratory procedures (samples taken, storage, transport).
- Each study country to describe the tests and kits used (and their sensitivity, specificity and positive predictive value for COVID-19 and influenza, and if necessary, for the detection of other respiratory viruses).
- Each study site/country to describe if the laboratory participates in QA/QC (Quality Assurance/Quality Control) schemes.
- Each study site/country to describe the selection of specimens (including Ct value threshold) and the procedures for genetic and antigenic characterisation, where appropriate.
- Each study site/country to describe sequencing methods and the process for selection of samples for further characterisation.
- Each study site/country to describe whether specimens are tested for other respiratory viruses (e.g. whether influenza continues to be tested systematically during the season and stops once the influenza season is over, or is only tested if the COVID-19 result is negative, etc.)

It is crucial that the vaccination status and date of vaccination variables are collected with the utmost care to ensure data completeness and quality. The definition of vaccination status will be updated considering evolving decisions related to vaccination programmes, such as the use of different products for subsequent doses as well as additional doses. It is highly recommended that sites collect the **brands of each COVID-19 vaccine received**, most importantly the brand of the first and last dose (to differentiate between primary series with single- vs two-dose vaccines).

It is also highly recommended that if a site cannot collect information on every prior dose, information should ideally be collected on:

- The first dose
- The penultimate dose
- The last dose.
- Each study site/country to describe the country COVID-19 vaccination recommendations and schedule, including specific recommendations by age/at-risk groups, and policy regarding timings between doses of primary course and booster doses, as well as the timing of vaccine rollout.
- Each study site to describe the COVID-19 vaccination variables they are collecting.

Exposure comparison groups

The above vaccination definitions can be used to estimate CVE in general. The table below focuses on exposed and reference groups to estimate CVE for the seasonal COVID-19 vaccination campaign of interest. The choice of comparison groups will depend on the analysis objectives and public health message of interest.

Table 3. Suggested comparison groups for CVE analysis

Exposed	Reference group	Analysis objective and restrictions
Vaccinated with any dose of COVID-19 vaccine as part of the COVID-19 vaccination campaign of interest	Unvaccinated in the COVID-19 vaccination campaign of interest	To estimate overall CVE of the current COVID-19 vaccination campaign in the general population, regardless of vaccination history. Both groups are restricted to those not vaccinated six months prior to the start of the vaccination campaign ^a
Vaccinated with any dose of COVID-19 vaccine as part of the COVID-19 vaccination campaign of interest	Unvaccinated in the COVID-19 vaccination campaign of interest, but vaccinated ≥6 months prior to the vaccination campaign	To estimate relative CVE of the current COVID-19 vaccination campaign; to understand the additional effect of the current COVID-19 vaccination campaign to prior vaccination ≥6 months earlier The exposed group is restricted to those not vaccinated six months before the start of the vaccination campaign ^a
Vaccinated with any dose of COVID-19 vaccine as part of the COVID-19 vaccination campaign of interest	Never vaccinated with COVID-19 vaccine	To estimate absolute CVE of the current COVID- 19 vaccination campaign Neither group is restricted by time since previous vaccination
Completely vaccinated with primary series plus at least one booster dose received as part of the COVID-19 vaccination campaign of interest	Completely vaccinated with at least primary series but with no doses received in the COVID-19 vaccination campaign of interest	To estimate relative (incremental) CVE of the current COVID-19 vaccination; to understand the additional effect of the current COVID-19 vaccination campaign Both groups are restricted to those not vaccinated in the six months prior to the start of the vaccination campaign ^a

^a The six months can be varied (e.g. three or five months) in sensitivity analyses. In a sensitivity analysis, vaccination six months prior to the start of the vaccination campaign can be substituted with six months prior to swab/onset.

^{*} The exact number of days will depend on the vaccine; this number may change and the protocol will be updated when more information is available.

Many other analyses may be of interest, including comparing CVE of specific number of doses (e.g. two booster doses) compared with those who were eligible for the specific number of doses, but did not receive it (e.g. the comparison of those receiving two booster doses to those receiving one booster dose, among those eligible for two booster doses).

> Each study site to describe the exposure and reference groups of interest for comparison.

Current seasonal influenza vaccine

- A SARI patient will be considered as vaccinated against influenza with any vaccine as part of the current
 influenza vaccination campaign if he/she has received one dose of the influenza vaccine ≥14 days before SARI
 symptom onset.
- A SARI patient will be considered as **unvaccinated** if he/she did not receive influenza vaccine as part of the current influenza vaccination campaign or if he/she was vaccinated after onset of symptoms. (Anyone vaccinated <14 days before SARI symptom onset will be excluded from the primary analysis).

Product-specific seasonal influenza vaccine

- A SARI patient is considered as vaccinated against influenza with a product-specific vaccine during the
 current season if he/she has received a vaccination with an influenza vaccine of a named product ≥14 days
 before symptom onset.
- A SARI patient is considered as **unvaccinated** if he/she did not receive influenza vaccine with a named product in the current season of if he/she was vaccinated after onset of symptoms. (Anyone vaccinated <14 days before SARI symptom onset will be excluded from analysis.)

Each study site/country to document COVID-19 and seasonal influenza vaccine products used.

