SARS-CoV-2 Severe acute respiratory syndrome – coronavirus 2

SES Socioeconomic status VE Vaccine effectiveness

Executive summary

The end of 2019 saw the emergence of a novel severe acute respiratory syndrome coronavirus 2 (SARS-CoV-2) causing coronavirus disease 2019 (COVID-19). As of October 2023, almost 276 million cases and more than 2.2 million deaths had been reported in the WHO European Region [1]. As of October 2023, eight vaccines (Comirnaty, COVID-19 Vaccine Valneva, Nuvaxovid [previously Novavax], Spikevax [previously COVID-19 vaccine Moderna], Vaxzevria [previously AstraZeneca], Jcovden [previously Covid-19 Vaccine Janssen], VidPrevtyn Beta [from Sanofi] and Bimervax [previously COVID-19 Vaccine HIPRA]), Nuvaxovid (NVX-CoV2373) and six adapted vaccines (Comirnaty Original/Omicron BA.1, Spikevax bivalent Original/Omicron BA.1, Comirnaty Original/Omicron BA.4-5, Spikevax bivalent Original/Omicron BA.4-5, Comirnaty Omicron XBB.1.5 and Spikevax XBB.1.5 have been authorised by the European Commission based on the scientific opinion of the European Medicines Agency (EMA) for use in the European Union, and many others are under rolling review [2].

Influenza viruses undergo frequent genetic and antigenic changes. The influenza vaccine is reformulated each year and annual re-vaccination is recommended. Observed influenza vaccine effectiveness (IVE) varies from year to year between population sub-groups (age groups, risk groups) and differs for the various influenza types, subtypes and genetic clades, and outcomes measured. Immunological correlates of protection are not well defined. In 2017, the EMA formally adopted new guidelines on influenza vaccines covering, inter alia, post-authorisation studies of vaccine effectiveness, including brand-specific IVE data [3].

The available vaccine products currently in use for EU/EEA immunisation programmes, the target groups for vaccination and the vaccination coverage all vary across countries. New vaccines are being developed for which limited or no effectiveness data are yet available in the EU. A comparison by vaccine type (adjuvanted vs non-adjuvanted, live attenuated vs inactivated, egg- vs cell-based, high vs standard dose), group (split virion, subunit, etc.) and product could provide essential information for vaccine recommendations and health economic assessments.

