2.1 Primary objective

The primary objective of this protocol is for it to be used to measure the direct effect (effectiveness) of overall and product-specific COVID-19 and influenza vaccines against SARI due to laboratory-confirmed SARS-CoV-2 and/or influenza in hospitalised patients, within each European country/site participating in both CVE and IVE and in a pooled, multi-country analysis. This will provide up-to-date information on the ability of COVID-19 and influenza vaccines to prevent severe disease under real conditions of use.

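### The product-specific influenza definition of unvaccinated lets vaccinated people into the reference group, which lowers product-specific IVE where several protective products are in use

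*Protocol*

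**What the plan says.** The primary objective (Section 2.1) covers "overall and product-specific COVID-19 and influenza vaccines", so product-specific IVE is a primary target. Section 2.2 repeats the product-specific aim for the secondary objectives.

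Section 3.8.1 then defines influenza vaccination status twice:

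- **Any vaccine.** A patient is unvaccinated "if he/she did not receive influenza vaccine as part of the current influenza vaccination campaign", or if vaccinated after onset.
- **Product-specific.** A patient is vaccinated "if he/she has received a vaccination with an influenza vaccine of a named product ≥14 days" before onset, and unvaccinated "if he/she did not receive influenza vaccine with a named product in the current season", or if vaccinated after onset. The one exclusion attached is: "Anyone vaccinated <14 days before SARI symptom onset will be excluded from analysis".

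The seasonal COVID-19 definition in the same section is also introduced as applying to product-specific vaccines. It takes as unvaccinated those with no dose at all in the campaign of interest.

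**The concern.** The two influenza definitions differ in who may serve as the reference. Under the any-vaccine rule, nobody vaccinated before onset in the current campaign can be in it. Under the product-specific rule some of them can. A patient given product B three weeks before onset has not received product A, is not caught by the 14-day exclusion, and so falls into the unvaccinated group when product A is analysed.

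If product B protects, the reference group is partly protected, the odds ratio for product A rises and its VE falls. This is bias, so a larger sample does not reduce it. Its size depends on coverage and product mix, which the Executive summary says vary across countries. Identical products could therefore give different country estimates and add artificial heterogeneity to the Q-test and I² planned in Annex 2. The Executive summary also expects product comparisons to inform vaccine recommendations and health economic assessments.

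**Working it through.** **Does another passage repair the rule?** Sections 2.1 and 2.2 ask for product-specific estimates without naming a reference group. Annex 2 (Stratified analysis) says only that the analysis by product will be stratified further. Section 3.13.2 allows other reference groups as optional sensitivity analyses, and its examples are for COVID-19. None removes recipients of other or unknown products.

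**Inputs.** Coverage of 30% to 90% among controls, a 1:1 ratio and 95% intervals are the protocol's (Sections 3.10 and 3.13.1). Section 1.2 describes seasonal influenza vaccines as moderately effective, with IVE that may vary by product. The protocol gives no product shares and no product VEs, so those below are assumptions.

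**The protocol's own figure.** It states none for this contrast, but Table 5 can be reproduced. With n = z² × [1/(p1(1−p1)) + 1/(p0(1−p0))] / [ln((OR+d)/OR)]² and p1 = OR·p0/(OR·p0 + 1 − p0), take OR 0.5, p0 0.5 and d 0.2:

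- p1 = 0.25/0.75 = 0.333, and the bracket is 4.5 + 4 = 8.5.
- n = 3.8415 × 8.5 / 0.3365² = 288.4, so 289 cases. Table 5 gives 289.

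**Bias, product-by-product reading.** Among controls let u be the share with no influenza vaccine and b the share given another product. With true odds ratios OR_A and OR_B against no vaccine:

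OR_obs = OR_A × (u + b) / (u + b × OR_B), and VE_obs = 1 − OR_obs.

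Assume two products, true VE 50% each. The last column lets product A's share of vaccinees run from 25% to 75%.

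| Coverage | u | b (equal split) | OR_obs | VE, equal split | VE, share 25% to 75% |
|---|---|---|---|---|---|
| 30% | 0.70 | 0.15 | 0.425/0.775 | 45.2% | 43.1% to 47.5% |
| 50% | 0.50 | 0.25 | 0.375/0.625 | 40.0% | 36.4% to 44.4% |
| 70% | 0.30 | 0.35 | 0.325/0.475 | 31.6% | 26.7% to 38.7% |
| 90% | 0.10 | 0.45 | 0.275/0.325 | 15.4% | 11.4% to 23.5% |

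For scale, Table 5 at VE 50%, coverage 50% and d 0.1 asks for 983 cases to obtain an interval of 40–58. The 10-point bias in the 50% row equals the whole lower half of that interval.

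**Other product VEs.** If the other product has VE 0, b no longer matters and the estimate is 50.0%. With true VEs of 40% and 60% and an equal split:

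- At 50% coverage the 40% product shows 1 − 0.6 × 0.75/(0.5 + 0.25 × 0.4) = 25.0%.
- At 50% coverage the 60% product shows 1 − 0.4 × 0.75/(0.5 + 0.25 × 0.6) = 53.8%.
- At 90% coverage the 40% product shows 1 − 0.6 × 0.55/(0.1 + 0.45 × 0.4) = −17.9%.

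**Any-named-product reading.** The same formula applies, with b now the share of controls vaccinated with an unrecorded brand. The protocol gives no figure for that share, so no size is calculated.

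**After the fix.** With b = 0, OR_obs = OR_A and the true 50% is recovered at every coverage.

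**The case against.** The text says *a* named product, not *the* named product. Literally, a recipient of product B has received a named product, meets the vaccinated definition and is not in the reference group. The neighbouring definitions use the ordinary meaning of unvaccinated, and the sentence itself contains a typing slip, so loose drafting is at least as plausible as a deliberate choice. This stands as a limit on the figures: the table holds only on the product-by-product reading. It does not remove the defect. On the literal reading, vaccinees of unrecorded brand are still counted as unvaccinated. Sites are also meant to write their own protocols from this core text (Section 1.5), so two readings can become two analyses.

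A reader might also infer that every product estimate is pulled towards zero and that the most-used product always looks better. The documents support neither. There is no bias with one product or with ineffective alternatives, and the estimate can pass zero.

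The market-leader effect depends on assumed equal VEs. At 70% coverage with a 70/30 split, two products of true VE 50% show 37.0% and 27.5%, a false gap of 9.5 points, but both the split and the equality are assumed. At 50% coverage, give the 70% product a true VE of 40% and the other 60%. The estimates become 1 − 0.6 × 0.65/0.56 = 30.4% and 1 − 0.4 × 0.85/0.71 = 52.1%. The true gap of 20 points grows to 21.7, against the leader.

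**Conclusion.** The point holds. As written, the rule puts some vaccinated patients into the reference group of a primary-objective contrast on either reading, and the protocol contains no correction.

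Where several protective products are in use, product-specific IVE is biased downward. On the product-by-product reading, with two products of true VE 50% and shares from 25% to 75%, the loss runs from 2.5 points (30% coverage, 75% share) to 38.6 points (90% coverage, 25% share). It can push the estimate below zero where the other products are clearly better and coverage is high. Unequal shares can also distort comparisons between products, in a direction that depends on the shares and the true VEs. Overall IVE is unaffected, because its own definition is sound.

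**What to change.** In Section 3.8.1, replace the product-specific definition so that a patient is unvaccinated if they received no influenza vaccine of any product in the current season, or were vaccinated after onset. Add that recipients of other or unknown products are excluded from that product's contrast, identified by flu_vaccbrand (Annex 1, Section G), and that their number is reported. They remain in the overall IVE analysis.

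No new data are needed and the exposed group is unchanged. The cost is a smaller reference group and some precision. With an equal two-product split, the reference share of controls falls from u + b to u: 0.85 to 0.70 at 30% coverage, 0.75 to 0.50 at 50%, and 0.55 to 0.10 at 90%. The loss is therefore small at low coverage and larger at high coverage, where overall IVE already relies on the same small reference group.
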